## **Research Synopsis**

**Study Population:** Medicaid or dual-eligible (Medicare-Medicaid) adults aged 21 years and older with multiple chronic conditions (MCC), including at least one physical health condition and at least one additional physical or behavioral health condition, beneficiaries/members of our partnering health care payer, and identified as having high and/or rising health care needs and at risk for unplanned health care use.

**Study Design:** A comparative effectiveness study using an individual-level, randomized design along with a pragmatic, mixed-methods approach to compare three strategies (e.g., in-person and telephonic supported care, technology-supported care, and optimal discharge planning care) all of which include evidence-based components of integrated care. Quantitative (e.g., self-report, claims, process) and qualitative (e.g., interviews) data will be collected across multiple timepoints during the study period.

Sample Size: We expect to enroll 1,400 individuals.

Study Duration: The contract period begins January 1, 2018 and concludes November 30, 2024.

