# **Statistical Analysis Plan**

#### Sample Size and Power Calculations

We will evaluate, based on a 20% attrition rate, a total of 1,120 participants at 12-month postenrollment data collection time point, which will be the main time point for the comparison of primary outcomes. We will use a randomization ratio of 2:2:1 (High-Touch; High-Tech; ODP, respectively) and, as such, estimate final sample sizes of n=448 for each active care strategy and n=224 for the ODP strategy. All calculations for the power estimates were done in PASS version 13. For the primary test for the trial, the power calculation is based on the comparison of the two primary care strategies (High-Touch and High-Tech) for the main outcome of hospital readmissions between the strategies, using a two-sample test of proportions; specifically we have 80% power to detect a difference between a readmission rate of 20% in the High-Touch care strategy versus 28% in the High-Tech care strategy. Additionally, for the overall differences between the three care strategies the given sample sizes yield 95% power; based on a chi-squared test.

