Our models will be based on an intent-to-treat principle as we do not expect large drop out or non-adherence. We will employ linear regression models for continuous outcomes, logistic regression for dichotomous outcomes, and Poisson regression or negative binomial models (in the case of over-inflated variance) for count outcomes. We will fit multivariate models with the key independent variable of interest being the main effect of treatment with main effects for additional covariates included to produce an adjusted estimate of the treatment effect. These covariates will be defined a priori and will be divided into two subgroups. The first set of clinically-important covariates will be included in all models including age, race, gender, insurance type, illness complexity, and socio-economic status. The second set of covariates will be defined as engagement in interventions, social support, health literacy, and technology literacy. To address Aim 2, separate models will be fit for each a priori defined heterogeneity of treatment group (HTE) subgroup of interest. As listed below, we will test the interaction of treatment with the covariate defining the HTE subgroup.

The objective of Aim 2 is to determine whether the intervention works better for some than for others. Our pre-specified analysis plan will examine differences in main outcomes for

several subgroups. These subgroups are determined by our stakeholders to be most relevant so that end results can meaningfully inform patients about what works best for whom, and in turn, better supports individuals with MCC as they navigate the health care system and make decisions about their care. Furthermore, in examining differential impact of the interventions based on these subgroups, providers, payers, and other decision makers can target resources in a manner that best meets the needs of those in services, reduces variations in practice, and improves health outcomes.

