We are only powering for the interactions with age, since we do not have any a-priori hypotheses about subgroup effects for the other variables. Those additional subgroups will clearly be labeled as exploratory and will only be examined further if the overall analysis is significant. We will conduct modeling as defined above to examine the HTE and will utilize contrasts from these regression models to make inferences about the heterogeneity. We will present both the treatment effect estimates, in terms of estimated odds or risk ratios for dichotomous or rate outcomes or the model coefficients for the continuous outcomes and measures of their variability in the form of confidence intervals. Two-sided tests of level 0.05 of the interactions between intervention and HTE subgroup will allow us to test the Aim 2 hypotheses.

For all the described models, we will focus on the 12-month outcome. Each of the above analyses will also be repeated using all follow-up outcomes collected as a secondary analysis using a mixed model with a random intercept to account for within-subject repeated measures and associated correlation. Significance tests from all regression models will all be assessed using likelihood ratio tests for logistic, Poisson, or, if applicable, negative binomial models or partial F-tests for linear regression.

Additionally, exploratory data analyses will include comparison of the following variables in the pre- versus post-COVID-19 time periods: a) demographics and primary outcomes at baseline, b) the primary outcomes over time, and c) patterns in missing data. If significant differences result, we will repeat the primary analysis by: a) adjusting for the demographic variables that can describe pre- and post-COVID-19 participants, b) include indicator variables for post-COVID-19 enrollment with and without interactions with time variables, and c) statistically account for missing patterns.

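### SF-36 and PAM: the primary 12-month regression names no missing-data method and rests on low expected drop-out, although 20% attrition is planned and a repeated-measures model is already in the plan as secondary

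*Combined protocol and SAP*

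**What the plan says.** - **Rationale.** Quantitative Analysis: "Our models will be based on an intent-to-treat principle as we do not expect large drop out or non-adherence".
- **Planned attrition.** Research Synopsis: "We expect to enroll 1,400 individuals". The section on sample size and power says: "We will evaluate, based on a 20% attrition rate, a total of 1,120 participants at 12-month postenrollment data collection time point". The per-arm figures follow: "estimate final sample sizes of n=448 for each active care strategy and n=224 for the ODP strategy".
- **Primary model.** Quantitative Analysis: "We will employ linear regression models for continuous outcomes". The same section focuses every model on the 12-month outcome. The covariates required in all models are age, race, gender, insurance type, illness complexity and socio-economic status. The baseline score is not among them.
- **Use of the other visits.** The analyses are "repeated using all follow-up outcomes collected as a secondary analysis using a mixed model with a random intercept".
- **Missing data.** No imputation, weighting, missing-data assumption or missing-data sensitivity analysis is given for the primary analysis. The one related item is a COVID-19 step that would account for missing-data patterns. It applies only if significant differences between periods are found, and it names no method. The PAM sensitivity analysis under Primary Outcome Measures concerns straight-lined answers.
- **Loss to follow-up.** Quantitative Analysis dates loss to the later of two events: stopping the surveys and losing coverage.
- **Survey schedule.** Study Design/Methodology and Compensation for Participation both have a 3-month self-report. Quantitative Analysis says there is no survey at Timepoint 2, which the compensation list identifies as 3 months.

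**The concern.** Intent-to-treat does not depend on low drop-out. The more drop-out is expected, the more the plan needs to say how missing outcomes are handled. Here low drop-out is the stated reason, the sample size allows for one participant in five being lost, and the primary model has no provision for them.

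A single-visit regression without such a provision can use only those who returned the 12-month survey. Their comparison remains fair if the reasons for drop-out act alike in the arms. High-Touch works in person and by telephone and High-Tech works through technology, so unequal reasons are plausible, though not shown. If low scorers leave one arm and not the other, the 12-month difference partly reflects who stayed. The 3- and 6-month scores carry information on those who left, but the primary model ignores them. A likelihood-based model that uses them is valid under the weaker missing-at-random assumption.

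Readmission is outside this point because it comes from claims.

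**Working it through.** **1. The plan's own figures**

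- Evaluable: 1,400 × (1 − 0.20) = 1,120. Split 2:2:1, this is 448 / 448 / 224, as stated. Randomized: 560 / 560 / 280. The gap is 1,400 − 1,120 = 280.
- PAM power, High-Touch v High-Tech: difference 8 − 4 = 4, SD 20.9, 448 per arm. Two-sided 0.05 is assumed, since the plan states it only for the interaction tests. SE = 20.9 × √(2/448) = 1.396; 4/1.396 = 2.864; Φ(2.864 − 1.960) = 81.7%, against 82% stated.

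The 20% loss is therefore built into the stated power. With 560 per arm the same formula gives SE 1.249 and power 89.3%. That is the ceiling if no information were lost; a longitudinal model would fall between the two.

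**2. How bias arises, by hand**

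In one arm, the mean among those who stay exceeds the full-arm mean by p × g, where p is the drop-out proportion and g is the stayer-minus-leaver gap in 12-month score. The bias of the unadjusted contrast is the difference in p × g between arms. Illustrations with assumed g:

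- 20% in both arms, gaps differing by 0.25 SD: 0.20 × 0.25 × 20.9 = 1.05 PAM points.
- 15% v 25%, gap 0.25 SD in both: (0.25 − 0.15) × 0.25 × 20.9 = 0.52 points.
- Same p and same g in both arms: zero.

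**3. Simulation for PAM**

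From the plan: SD 20.9, difference 4, 560 per active arm, 20% drop-out in each arm. Assumed: drop-out before 12 months depends on the 6-month score, and visit correlation is 0.5 to 0.7. In the one-arm case the log-odds of drop-out are −0.5 to −1.2 per SD. The likelihood-type estimate regresses the 12-month score on all earlier visits within arm and averages over everyone randomized.

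| Selection by 6-month score | 12-month regression adjusted for baseline: bias |
|---|---|
| One arm only | about 0.4 to 1.0 points |
| Both arms, unequal (−0.5 v −0.8, or −0.8 v −1.2) | about 0.2 to 0.3 |
| Both arms, equal | about 0 |

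In the one-arm case the likelihood-type bias was under 0.1. As a share of the planned effect, 0.4/4 = 10% and 1.0/4 = 25%.

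**4. Dependence on the form of the outcome**

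- Without the baseline score, which the covariate list omits, the one-arm case gives about 1.0 to 2.9 points.
- The power section describes increases in score. If the outcome is change from baseline and all visit correlations are equal, the bias is about zero. With an assumed 6-to-12-month correlation of 0.7 and baseline-to-6-month correlation of 0.5, it is about 0.4 to 0.8.

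**5. SF-36**

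Rescaling to SD 10: 0.4 × 10/20.9 = 0.19 and 1.0 × 10/20.9 = 0.48 points. The planned difference is 11 − 5 = 6, so this is 3% to 8% of it.

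**The case against.** **A reader might infer that the plan declares a complete-case analysis.** It does not. The term never appears, and the intent-to-treat sentence does commit the trial to analysis by assigned arm. What the text shows is silence on missing outcomes. Use of 12-month responders only is the natural consequence of a single-visit regression with no stated provision, but it is an inference.

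**A reader might infer a flat contradiction.** The 20% is a sample-size allowance, and the plan does not define what counts as large drop-out. Tension that needs reconciling is as far as the text goes.

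**A reader might infer that 280 participants will be excluded.** The figure is a planning number. Under the rule that the later event defines loss, someone who stops surveys but keeps coverage is not lost to follow-up, yet has no SF-36 or PAM score. Missing surveys may exceed 20%; the documents give no figure.

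**The mixed model is already planned.** True, and its result will presumably be reported. What remains is which result is primary, and a specification that so far consists of a random intercept on follow-up outcomes.

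**The bias is built on chosen assumptions.** This stands. Selection in one arm only is an extreme case, and nothing in the documents supports it over the milder ones. The simulation also gives every leaver complete 3- and 6-month scores, which is the best case for the remedy, and it did not run the plan's random-intercept model.

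**Conclusion.** The point holds as an inexpensive improvement to the SF-36 and PAM analyses. The stated reason for intent-to-treat does not fit the planned attrition, the primary model has no missing-data method, and a model that uses more of the scheduled data is only secondary.

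The size is conditional. On the assumptions shown, the PAM bias with baseline adjustment runs from about zero (equal selection), through 0.2 to 0.3 points (unequal selection in both arms), to 0.4 to 1.0 points (selection in one arm only). It is larger if the 12-month score is analysed without baseline. SF-36 is less exposed relative to its planned effect. A reader might take the top of the range as the expected bias in this trial; the documents support neither that nor any direction. That the answer turns on an unstated drop-out mechanism and outcome form is the reason to specify the handling in advance.

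**What to change.** 1. First reconcile the statement that Timepoint 2 has no survey with the 3-month self-report in Study Design/Methodology and Compensation for Participation. This settles which visits enter the model.
2. For SF-36 and PAM, make a likelihood-based repeated-measures model primary. Include all randomized participants with any score, the baseline score, treatment-by-visit terms and unstructured covariance, and report the 12-month contrast. State whether baseline is a response or a covariate: participants with a baseline score only remain in the likelihood only if it is a response.
3. Keep the 12-month linear regression as a sensitivity analysis.
4. Add a missing-not-at-random sensitivity analysis, because the new primary model still assumes missing at random.
5. Delete the low-drop-out rationale, and report the number with a 12-month survey by arm separately from loss to follow-up.

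Cost: SAP text only, with no new data collection and no change in sample size. The primary model becomes somewhat more complex. The existing mixed model must be respecified as well as relabelled, and the Aim 2 interaction models for these two outcomes must be written to match.

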## **Secondary Outcome Measures**

Subsequent rehospitalization will be measured using an all-cause readmission rate existing in UPMC ISD inpatient claims for physical and behavioral health service use within 30 days and again at 12 months, following the index inpatient admission. Inpatient and ED visits that were adjudicated and reclassified as Observation visits will be separately explored at 12 months.

Functional status will be measured using the PROMIS Physical Functional Form – Short For 6b which is a brief self-report tool that assesses functional impairment in everyday tasks, household chores, and walking using a 5 point Likert scale.

Quality of life will be measured using the Quality of Life Enjoyment and Satisfaction Questionnaire (Q-LES-Q-18), which is an 18-item, self-administered questionnaire monitoring enjoyment in several domains (physical health, subjective feelings, leisure time activities, social relationships).

Care satisfaction will be measured using the Patient Assessment of Chronic Illness Care (PACIC), a 20-item survey designed to provide an assessment of important aspects of care for chronic illness patients, including specific actions or qualities of care that patients report experiencing in the service delivery system and their satisfaction level.

Emergent care use will be measured using existing behavioral and physical health claims data from the UPMC ISD data warehouse determining participant frequency of emergent service use over 12 months.

Engagement in primary, specialty, mental health care will be measured using existing behavioral and physical health claims data from the UPMC ISD data warehouse determining participant frequency of non-acute visits for participants over 12 months.

Gaps in care will be assessed using Healthcare Effectiveness Data and Information Set (HEDIS) quality metrics that will be compiled using existing behavioral and physical health claims data from the UPMC ISD data warehouse. Gaps in care will be assessed for six of the most common chronic diseases present among our target population, including: asthma, chronic obstructive pulmonary disease, congestive heart failure, coronary artery disease, diabetes, and depression.

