## Covariates

Engagement in interventions will be assessed using the automatically generated usage statistics and administrative/ utilization data routinely collected for non-research purposes as part of insurance claims processing and existing payer-provider service delivery.

Patient characteristics will be obtained through self-report data and existing secondary administrative data on age, gender, race/ethnicity, and insurance type.

Technology/digital literacy will be measured using a series of questions from the Health Information National Trends Survey (HINTS) to assess comfort and experience with use of different. communication channels, including the Internet, to obtain vital health information for themselves and their loved ones.

Social support will be measured using the Interpersonal Support Evaluation List (ISEL), a 12-item measure designed to assess the perceived availability of three types of social support (appraisal, belonging, and tangible).

Health literacy will be measured using the first ten items of the All Aspects of Health Literacy Scale (AAHLS), a 13-item survey designed to assess functional, communicative, and critical health literacy. The final three items on the AAHLS are part of an 'empowerment scale' that is not related to the outcomes of this study.

Illness complexity will be measured using the age-adjusted Charlson Comorbidity Index (CCI) which was developed as a prognostic burden of comorbid disease and is currently used by the UPMC ISD. A score will be computed at baseline based on the previous 12 months of claims, adding assigned weights for specific diseases as classified by using International Classification of Diseases (ICD) diagnoses on claims records, and age adjusting by adding 1 point for every decade over 40 to the CCI score.

Socioeconomic status will be measured using the Area Deprivation Index (ADI), which uses 17 different socioeconomic indicators to determine a deprivation score for a given neighborhood. Scores are reported in the form of quintiles, with a higher quintile indicating a higher degree of deprivation.

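### The models for the claims outcomes omit prior-year service use, so a cheap gain in power, probably modest for the primary readmission test, is forgone

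*Combined protocol and SAP*

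**What the plan says.** Under Quantitative Analysis, the combined protocol and SAP plans logistic regression for binary outcomes and Poisson or negative binomial regression for counts, with covariates chosen in advance in two sets. On the first set it says: "The first set of clinically-important covariates will be included in all models including age, race, gender, insurance type, illness complexity, and socio-economic status". Social support, health and technology literacy, and engagement with the intervention make up the other set. Engagement is measured after randomisation, so it does not stand in for prior use.

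Under Covariates, illness complexity is an age-adjusted Charlson score: "A score will be computed at baseline based on the previous 12 months of claims". The score counts diagnoses and age, not how often care was used.

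The claims outcomes are readmission (primary at 90 days; secondary at 30 days and 12 months), engagement in non-acute care, and emergent care, the last measured by "determining participant frequency of emergent service use over 12 months".

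Under Sample Size and Power Calculations, the primary comparison is powered "using a two-sample test of proportions": "we have 80% power to detect a difference between a readmission rate of 20% in the High-Touch care strategy versus 28% in the High-Tech" strategy. No power is stated for the 12-month count outcomes. Stratification uses gender, insurance type and technology literacy. The COVID-19 re-analysis adds demographics, enrolment-period indicators and missing-data patterns. Neither brings in prior use.

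**The concern.** Earlier use of a service is a natural baseline predictor of later use of the same service. The trial recruits members because they are at high risk of heavy use, commits to adjusted estimates, and already works from a year of prior claims to build one covariate. Leaving prior counts out of the models for later counts is therefore an unexplained gap.

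What is at stake is efficiency. The primary readmission comparison has no slack: 447 per arm are needed for 80% power and 448 are expected. The age-by-treatment interaction for readmission is put at 79.8%. Timing also matters. The SAP says that analyses added during the study will be labelled post hoc, so a model with prior use that is not written in beforehand would carry less weight.

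**Working it through.** **Inputs from the documents.** Enrolment 1,400; "based on a 20% attrition rate, a total of 1,120 participants"; "We will use a randomization ratio of 2:2:1"; and "estimate final sample sizes of n=448 for each active care strategy and n=224 for the ODP strategy". Check: 1,400 × 0.8 = 1,120, and 1,120 × 2/5 = 448. Readmission rates are 20% and 28%. Two-sided 0.05 is stated only for the interaction tests; it is assumed here for the primary test.

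**Step 1: reproduce the stated power.** Power = Φ{(Δ − 1.96·SE0)/SE1}, with pooled rate 0.24.

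- SE0 = √(2 × 0.24 × 0.76/448) = 0.02854
- SE1 = √[(0.20 × 0.80 + 0.28 × 0.72)/448] = 0.02841
- (0.08 − 0.05593)/0.02841 = 0.847, so power = 80.2%

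The stated 80% holds. It also reproduces with unpooled variance (80.4%) and the arcsine form (80.3%); with a continuity correction it is 77.9%.

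**Step 2: add a prognostic covariate.** Let R² be the share of outcome variance that prior use explains beyond the covariates already in the model. The documents do not give it, so it is assumed. As an approximation, effective n per arm = 448/(1 − R²).

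| Assumed R² | Effective n per arm | Power |
|---|---|---|
| 0 | 448 | 80.2% |
| 0.02 | 457 | 80.9% |
| 0.05 | 472 | 82.1% |
| 0.10 | 498 | 84.1% |
| 0.15 | 527 | 86.1% |
| 0.20 | 560 | 88.1% |

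In sample-size terms, R² of 0.02 to 0.20 equals 1/0.98 − 1 = 2% to 1/0.80 − 1 = 25% more participants.

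**Step 3: check with the planned type of model.** Logistic likelihood ratio tests were simulated with 448 per arm, marginal rates of 20% and 28%, and a normally distributed prior-use score (4,000 runs per setting, Monte Carlo standard error about 0.6 points). No other covariates were included.

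| AUC of score | R² | Unadjusted | Adjusted |
|---|---|---|---|
| 0.50 | 0 | 80.1% | 80.0% |
| 0.58 | 0.014 | 80.8% | 81.4% |
| 0.64 | 0.038 | 81.1% | 83.0% |
| 0.68 | 0.072 | 80.8% | 83.6% |
| 0.73 | 0.112 | 81.7% | 85.9% |
| 0.76 | 0.156 | 79.5% | 86.0% |

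The gain is about 1 to 6 points, and nothing material is lost when prior use is not prognostic. A further simulation, with an assumed comorbidity-and-age score already in the model, gave a gain of about 2 to 6 points.

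**Step 4: where the gain appears.** The unadjusted odds ratio is (0.28/0.72)/(0.20/0.80) = 1.56. With prior admissions simulated as negative binomial (assumed mean 1.5, dispersion 1) and odds ratios per admission of 1.3, 1.5 and 1.8, the conditional treatment odds ratio became about 1.60, 1.66 and 1.76. The standard error of its logarithm rose from 0.159 to 0.164, 0.171 and 0.181. Power rises because the conditional odds ratio moves further from 1 than its standard error grows.

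**Step 5: count outcomes.** If prior and later counts correlate at ρ (assumed), a linear approximation multiplies the variance by 1 − ρ². From a notional 80%, power = Φ{(1.960 + 0.842)/√(1 − ρ²) − 1.960}. This gives 83.6%, 86.4%, 89.9% and 93.9% for ρ = 0.3, 0.4, 0.5 and 0.6. The planned models are Poisson or negative binomial, so these figures are only indicative.

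**The case against.** The strongest reply is that nothing in the plan is wrong. The promised power is reached without this covariate, type I error is unaffected, and the choice of prognostic covariates is partly judgement. That stands.

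The right comparator is also not an unadjusted test. The planned model already holds age, the Charlson score, insurance type and socioeconomic status, so only variance explained beyond these counts. Every participant has a recent inpatient stay, which may narrow the spread of prior use. That stands too, and favours the lower end of the range.

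A reader might infer that adjustment would tighten the confidence interval for readmission. For the planned odds ratio it would not, as step 4 shows. The estimand also shifts, because the odds ratio becomes conditional on prior use; odds ratios from the planned models are already conditional on other covariates.

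A reader might also infer that a complete prior-use file exists for everyone. The documents show only that a diagnosis score is computed from a year of earlier claims. The extraction described under Study Design/Methodology concerns service use during enrolment. Eligibility accepts cover through physical and/or behavioural health payers and sets no minimum prior coverage, so some histories may be incomplete.

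Finally, the word introducing the first covariate list could be read as non-exhaustive. But the covariates are to be defined a priori, and prior use is named nowhere.

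**Conclusion.** The omission is real and cheap to repair, but it is an opportunity forgone. It would be wrong to conclude that the trial is underpowered or the readmission test biased: 80% is met as stated.

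For the primary readmission test, power would go from about 80% to 81–88% for an assumed incremental R² of 0.02 to 0.20, with the lower end more plausible. The documents give no correlation between prior and later use, so nothing in them supports calling it a strong predictor. For the 12-month counts the gain could be larger, but it rests wholly on the assumed correlation. The recommendation survives this uncertainty because, when prior use carried no information, the simulated cost was negligible.

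**What to change.** Under Quantitative Analysis, before any unblinded analysis, add to the first covariate set, for each claims outcome, the matching count over the prior 12 months: inpatient admissions for readmission, emergency visits for emergent care, and non-acute visits for engagement. State the form, for example log(1 + count).

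End the look-back before the index admission. Enrolment may follow discharge by up to 30 days while primary readmission is counted from that discharge, so a window running to enrolment could let an event serve as both covariate and outcome. The rule also keeps the qualifying stay out of the count.

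Add months of prior coverage, or a missing-history indicator. A months-covered term alone will not reveal a payer type that is absent from the record. State that the readmission odds ratio is conditional on the listed covariates.

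The cost is a few sentences of SAP text and a few more variables derived from claims, with no new contact with participants. The small downside is that some histories will be incomplete.
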